## 1.0 Background (Limit 1,000 words):

**Provide the scientific or scholarly background for the proposed Human Research. Discuss relevant prior experience or preliminary data (e.g., existing literature).**

Multiple studies have shown ketamine to be safe and effective agent for acute pain syndromes [1,2,3]. Rattlesnake envenomations classically result in severe pain that can be difficult to control, despite use of opioids, non-opioid analgesics, and positioning techniques, including splinting and elevation. Furthermore, the ongoing opioid epidemic pushes clinicians to explore non-opioid agents to avoid unnecessary exposure of patients to these high-risk medications. At least one small study has shown ketamine to be safe in rattlesnake envenomated patients.

## 2.0 Lay Summary:

**Provide a brief description of the proposed research using terms that someone who is not familiar with the science or discipline can understand.**

This is a pilot study to evaluate pain responses from two different approved medications (ketamine and fentanyl) in the treatment of pain after rattlesnake envenomation (RSE). Both medications are currently used in standard practice to treat both acute and chronic pain and are options for pain management after RSE. Multiple studies exist showing ketamine to be both safe and effective for the treatment of acute pain, and to be as good as or better than opioids for this indication. The specific comparison of ketamine to fentanyl, however, has never been studied for the treatment of acute pain after rattlesnake envenomation in the United States. We plan to measure pain scores after a single dose of ketamine or fentanyl in patients shortly after being envenomated, followed by continued treatment of pain guided by the treating doctor. There will be no restrictions on additional pain medications given and no other changes to the treatment of these patients during their hospitalization. This research is important because pain after RSE can be difficult to control and may require frequent, high doses of opioids for several days. An effective non-opioid medication would be helpful both to better-control pain and to reduce exposure to opioids in this patient population. This study will compare patient-reported pain scores after receiving a single dose of ketamine or fentanyl in patients with rattlesnake bites who have been admitted to the toxicology service at Banner – University Medical Center Phoenix (BUMCP).

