## 3.0 Purpose:

**Describe the purpose, specific aims, objectives, questions to be answered, hypotheses, and/or primary and secondary study endpoints of the Human Research.**

The purpose of this study is to evaluate differences in pain levels following a single administration of fentanyl or ketamine to treat pain after rattlesnake envenomation. The aim is to assess pain scores prior to medication administration, then 15, 30, 60, and 120 minutes after single medication administration. Primary endpoint is pain score at 30 minutes after medication administration. Secondary endpoints are pain scores at additional time points, need for rescue medication, adverse medication effects, and patient pain satisfaction scores at discharge.

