## 6.0 Study Population:

### 6.1 Select all the categories of participants included in the research:

# IRB Protocol for Human Subjects Research

 Healthy adults	 Non-English-speaking subjects
 Non-healthy adults	 UA staff/faculty
 Children (under 18 years old) *	 UA students
 Pregnant women, neonates, and/or fetuses*	 Banner employees
 Prisoners*	 Refugees
 Native Americans, Alaskan Native, and Indigenous Populations*	 Other – please explain: All patients admitted to BUMCP toxicology service diagnosed with RSE
 Adults unable to consent (i.e., cognitively impaired adults) *	

**6.2 For each of the above selected categories, describe the inclusion and exclusion criteria. Indicate age range, gender, and ethnicity.**

Inclusion Criteria

1. Ages  $\geq$  18 years.
2. Able to speak and understand English.
3. RSE requiring IV pain medication for NRS pain score  $> 5$ .
4. No allergy to ketamine or fentanyl.
5. Ability to provide informed consent.
6.  $\leq$  24 hours from envenomation.

Exclusion Criteria

1. Pregnant or lactating.
2. Prisoners.
3. Refugees.
4. History of schizophrenia.
5. Clinically intoxicated.
6. On buprenorphine therapy.
7. History of uncontrolled hypertension.
8. Increased intracranial pressure.
9. Systemic envenomation.

**6.3 Describe the total number of subjects to be enrolled locally. If obtaining specimens, specify the maximum number of specimens needed for this project.**

40 participants.

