# IRB Protocol for Human Subjects Research

Gender

History

Weight

PMH

Allergies

Home medications

Substance use

If yes what? alcohol, opioid, stimulant, hallucinogen, marijuana, tobacco

Clinical/treatment

HPI including time of bite, type of snake (if known), field treatments, ED treatment, vital signs, labs, imaging, medications administered and time (including analgesia), antivenom administration (time from bite to AV, type of AV, doses, and vials), procedures (i.e., splinting), measurements, adverse events, LOS

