## Statistical Methods

Differences between pain scores at time zero (before drug administration) and at time 30 minutes will be compared between the fentanyl and ketamine group using a Wilcoxon Signed Ranks Test, using a two-tailed alpha of 0.05.

Significant clinical difference will be defined as an absolute difference between groups of greater than 1.3 (using confidence interval of 95%). This difference is commonly accepted as the minimum clinical difference in subjective pain scales [5].

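### The primary comparison makes no use of the recorded analgesia given before the study dose, which costs some precision and leaves chance imbalance unadjusted at about 20 patients per arm

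*Combined protocol and SAP*

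**What the plan says.** - **Entry (section 6.2).** Patients qualify up to "24 hours from envenomation", with "RSE requiring IV pain medication for NRS pain score" above 5. The exclusions that come nearest to earlier drug exposure are "On buprenorphine therapy" and clinical intoxication. No minimum time since the last opioid and no limit on earlier analgesia is stated.
- **Data (section 8.2, clinical and treatment items).** Treatment in the field and in the emergency department is abstracted, as are "medications administered and time (including analgesia".
- **Endpoint and analysis.** Section 3.0 states: "Primary endpoint is pain score at 30 minutes after medication administration". Statistical Methods states: "Differences between pain scores at time zero (before drug administration) and at time 30 minutes will be compared between the fentanyl and ketamine group". It names a Wilcoxon signed-rank test at two-sided 0.05 and a between-group threshold of 1.3 points. It names no covariate, stratum or sensitivity analysis.
- **Allocation and size.** Assignment is 1:1 from a block list, with no mention of stratification by earlier opioid use. The total is 40, set by one year's availability.
- **Care after the study dose (section 2.0).** The Lay Summary states: "There will be no restrictions on additional pain medications given and no other changes to the treatment of these patients during their hospitalization". It says nothing about analgesia before time zero.

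**The concern.** The stated aim is to compare pain after one dose of each drug. Two patients can both score 7 at time zero with different histories: one has had no opioid, and the other had one shortly before. Their scores may drift differently over the next 30 minutes for reasons unrelated to the study drug. Subtracting the time-zero score removes the starting level but not that drift.

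The plan permits this situation and collects the data that would describe it, but leaves the data out of the primary comparison. If earlier opioid use predicts the 30-minute change, ignoring it widens the error of the between-arm difference. It also leaves a chance imbalance between two small arms uncorrected. The variance estimate passed to the larger study mentioned under Group Size Calculations would carry the same excess. If adjustment is decided only after the data are seen, the choice of look-back and model is open to challenge.

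**Working it through.** The plan's figure of 40 comes from availability, not from a power formula, so there is no sample-size calculation to reproduce.

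**Inputs from the documents:** 40 patients at 1:1, so about 20 per arm; threshold 1.3; two-sided alpha 0.05.

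**Inputs assumed, because the documents give none:** share with a recent opioid p = 0.5 (range 0.3 to 0.7); effect of that opioid on the 0-to-30-minute change c = 1 to 2 NRS points, the same in both arms; residual SD s = 2 (also 2.5).

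**1. Bias.** With p and c the same in both arms in expectation, the expected between-arm shift is c × (p − p) = 0. A simulation (4,000 runs, 20 per arm, p = 0.5, s = 2, rank-sum test) gave type I error of 4.8% for c = 1 and 4.3% for c = 2, with a mean shift of about 0.01 points.

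**2. Chance imbalance.** The SD of the difference in proportions is √(2p(1 − p)/20).
- p = 0.5: √(2 × 0.25/20) = 0.158. The 95% shift is 1.96 × 0.158 × c, which is ±0.31 for c = 1 and ±0.62 for c = 2.
- p = 0.3 or 0.7: √(2 × 0.21/20) = 0.145. The shift is ±0.28 for c = 1 and ±0.57 for c = 2.
- Exact binomial, p = 0.5: the arms differ by at least 4 exposed patients with probability 0.268, and by at least 5 with probability 0.154. For p = 0.3 or 0.7, the probability of at least 4 is 0.226.

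**3. Precision.** Total SD = √(s² + c²p(1 − p)), and the standard error is SD × √(2/20). For s = 2 and p = 0.5:
- Adjusted: SD 2.00, SE 0.632, 95% half-width 1.24.
- Unadjusted, c = 1: SD √4.25 = 2.06, SE 0.652, half-width 1.28.
- Unadjusted, c = 2: SD √5 = 2.24, SE 0.707, half-width 1.39. Variance is 25% higher, so 40 patients carry the information of 40/1.25 = 32.

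The shifts in step 2 are part of these half-widths, not additional to them: √(1.24² + 0.62²) = 1.39.

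**4. Power for a 1.3-point difference.** Normal approximation for two means: Φ(1.3/SE − 1.96).

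| Residual SD | Unadjusted, c = 1 | Unadjusted, c = 2 | Adjusted |
|---|---|---|---|
| 2 | 51% | 45% | 54% |
| 2.5 | 36% | 33% | 38% |

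The adjusted column ignores the small cost of estimating the covariate effect, so it is slightly favourable to adjustment.

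**The case against.** The strongest reply is that randomization already deals with this. An additive effect common to both arms cancels in the between-arm difference, and chance imbalance is part of the sampling error that a two-group test allows for. That stands. The ±0.3 to ±0.6 is a component of the ordinary error, not a bias to be set on top of it.

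Several stronger readings are tempting, and the documents do not support them:
- A reader might take "There will be no restrictions on additional pain medications given and no other changes to the treatment of these patients during their hospitalization" as licence for unlimited analgesia before dosing. The preceding sentence has the single study dose "followed by continued treatment of pain guided by the treating doctor", so the statement concerns later care.
- A reader might infer that opioids are still acting at time zero. The plan permits this but gives no frequency or timing. The 30 minutes for consent and 5 for randomization in section 8.3 are a subject's time commitment, and nothing there says that analgesics are given in that interval.
- A reader might infer that earlier opioids hide a real difference, or that enrolling patients who still hurt after opioids works against the fentanyl arm. The first confuses added noise with bias. The second is possible effect modification in the population that the trial chose to study; no data in the documents bear on it, and a main-effect covariate would not remove it.

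Two further objections stand in part. A recent opioid could be taking effect or wearing off, so a yes/no flag may average opposite effects and predict little. And a rank test as written takes no covariate, so adjustment means naming a different method. The pilot label weakens the case less, because the plan still specifies a formal test and a 1.3-point criterion.

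**Conclusion.** The gap is confirmed and is one of analysis, not of data capture: entry runs to 24 hours without a limit on earlier analgesia, drug and time are recorded, and the primary comparison uses neither. The consequence is lost precision and uncorrected chance imbalance, not built-in bias. A reader might conclude that the result could not be read as the effect of the study dose; under sound randomization, that does not follow.

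If half the patients are exposed and the effect is 1 to 2 points, the 95% chance shift is about ±0.3 to ±0.6 points against 1.3. With residual SD 2, adjustment recovers about 3 to 9 percentage points of power (54% against 51% to 45%); with SD 2.5, about 1 to 4 points from the unrounded figures. All carry-over inputs and SDs are assumptions. If earlier opioid use does not predict the change, the gain is nil. This is a modest, inexpensive improvement that should be written down before the data are examined.

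**What to change.** In Statistical Methods, prespecify one baseline factor from data already abstracted: any opioid given in a fixed look-back before time zero (yes/no), with the length of the look-back stated (60 minutes, for example). Use it in one of two named ways:
- as the stratum in a stratified two-group rank-sum (van Elteren) test of the 0-to-30-minute change; or
- as a covariate, with baseline NRS, in a linear model of the 30-minute score. This gives an adjusted between-arm difference with a 95% interval to set against 1.3.

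Tabulate by arm the last analgesic before time zero, its dose and time, and the time from bite to study drug. Add a supportive analysis in patients with no opioid in the look-back.

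**Cost.** Analysis wording only, with no new data collection and no change to care. The planned unstratified test is replaced, the look-back cut-off is arbitrary, a little precision is lost if the factor is not prognostic, and the supportive set will be small. Whether analgesia before dosing should be restricted is a clinical matter outside this point.

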## 3.0 Purpose:

**Describe the purpose, specific aims, objectives, questions to be answered, hypotheses, and/or primary and secondary study endpoints of the Human Research.**

The purpose of this study is to evaluate differences in pain levels following a single administration of fentanyl or ketamine to treat pain after rattlesnake envenomation. The aim is to assess pain scores prior to medication administration, then 15, 30, 60, and 120 minutes after single medication administration. Primary endpoint is pain score at 30 minutes after medication administration. Secondary endpoints are pain scores at additional time points, need for rescue medication, adverse medication effects, and patient pain satisfaction scores at discharge.

**Primary hypothesis**

There will be no difference in pain responses in the two groups.

Fentanyl and ketamine are commercially available and used as FDA approved for the management of pain in the United States.

# IRB Protocol for Human Subjects Research

## 4.0 Funding Information:

Indicate all sources of funding for the project, including gift funds, departmental funds, or other internal funding. For each funder, list the name of the funder, and the institutional proposal number or award number you received from Sponsored Projects. For externally funded projects, the information below should match the Study Funding Sources in [eIRB](#).

 No Funding	
 Federal Funding , including flow-through federal funding (i.e., NIH, NSF, DoD, etc.)	Name of funding source:
	Institutional Proposal or Award Number:
	eDoc # (for multi-site projects):
 Industry Funding	Name of funding source:
	Institutional Proposal or Award Number:
	eDoc #:
 Foundation Funding	Name of funding source:
	Institutional Proposal or Award Number:
 Department Funding	Name of funding source:
 Gift Funding	Name of funding source:
 Other	Name of funding source:

## 5.0 Resources Available to Conduct the Human Research:

**Describe the resources (facilities, time, emergency resources, etc.) available to recruit, consent, conduct study procedures, and analyze data.**

All recruitment, consent, study procedures and data analysis will be conducted by study investigators at BUMC Phoenix.

## 6.0 Study Population:

### 6.1 Select all the categories of participants included in the research:

# IRB Protocol for Human Subjects Research

 Healthy adults	 Non-English-speaking subjects
 Non-healthy adults	 UA staff/faculty
 Children (under 18 years old) *	 UA students
 Pregnant women, neonates, and/or fetuses*	 Banner employees
 Prisoners*	 Refugees
 Native Americans, Alaskan Native, and Indigenous Populations*	 Other – please explain: All patients admitted to BUMCP toxicology service diagnosed with RSE
 Adults unable to consent (i.e., cognitively impaired adults) *	

**6.2 For each of the above selected categories, describe the inclusion and exclusion criteria. Indicate age range, gender, and ethnicity.**

Inclusion Criteria

1. Ages  $\geq$  18 years.
2. Able to speak and understand English.
3. RSE requiring IV pain medication for NRS pain score  $> 5$ .
4. No allergy to ketamine or fentanyl.
5. Ability to provide informed consent.
6.  $\leq$  24 hours from envenomation.

Exclusion Criteria

1. Pregnant or lactating.
2. Prisoners.
3. Refugees.
4. History of schizophrenia.
5. Clinically intoxicated.
6. On buprenorphine therapy.
7. History of uncontrolled hypertension.
8. Increased intracranial pressure.
9. Systemic envenomation.

**6.3 Describe the total number of subjects to be enrolled locally. If obtaining specimens, specify the maximum number of specimens needed for this project.**

40 participants.

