# IRB Protocol for Human Subjects

## Research

 Face to face	 Social media
 Flyers	 SONA System
 In person presentations	 TV, Radio, Print
 Online advertisements	 Other – please explain: Click or tap here to enter text.
 Phone calls	

**6.5 Explain the recruitment process. Describe how potential subjects will be identified, where recruitment will take place, when recruitment will occur, and the methods that will be used to recruit individuals.**

Subjects will be identified by the study investigators who are BUMCP physician medical toxicologists and care for RSEs at BUMCP. Subjects will be screened and interviewed using the inclusion/exclusion criteria and if eligible, be asked if they would like to participate in the study. The informed consent form will be reviewed by a trained investigator with the subject/legally authorized representative. To include the voluntary nature of the study, risks/benefits, and study procedures will be explained in detail. Adequate time to review the informed consent form will be given and all questions and concerns will be addressed. The subject/legally authorized representative be given a copy of a signed consent if they choose to participate.

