## Instrument Administration

Patients meeting inclusion criteria will be identified by the study investigators who are BUMCP physician medical toxicologists and care for RSEs. Informed consent, randomization and data abstraction/collection will be obtained by the investigators. Pain scores will be obtained at bedside by investigators at the following intervals; prior to medication administration (zero) and after medication administration at the following intervals 15, 30, 60, and 120 minutes, and a patient satisfaction score at discharge.

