## Randomization

Block randomization – A randomization list has been developed that will be used to assign drug (form: ‘Master List-Randomization’). Following enrollment, the subject will be assigned in sequential order. Each block will alternate between each drug (ketamine or fentanyl). Subjects will have 50/50 chance of being assigned to ketamine or fentanyl and will be blinded to which drug they received during the study. After participation in study (meaning they have completed their patient satisfaction score at discharge) subjects will be told what medication they received during the study.

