## Data Monitoring

Ongoing data monitoring will be performed by investigators throughout the duration of the study period.

**8.3 Specify the total estimated time commitment for subject participation, and the estimated time commitment for each activity.**

Total time commitment	95 minutes
Study procedures	Time to complete
Informed consent	30 minutes
Randomization	5 min
Assessment of pain scores at bedside	
Prior to drug administration (zero)	10 min
15 min after drug	10 min
30 min after drug	10 min
60 min after drug	10 min
120 min after drug	10 min
Patient pain satisfaction question at discharge	10 min

**8.4 If any biological specimens (blood, urine, tissue, etc.) are being collected for research, state the amount, method, frequency, and type of specimen to be collected and what the specimen will be used for.**

NA

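### The NRS >5 entry criterion is not tied to the time-zero score, so patients at 5 or below can be randomized and dosed, and the primary baseline can be scored after the arm is known

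*Combined protocol and SAP*

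**What the plan says.** Inclusion criterion 3 in Section 6.2 is "RSE requiring IV pain medication for NRS pain score" above 5. It names neither a time nor an assessment. The only time limit on entry is criterion 6, at most "24 hours from envenomation".

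Section 6.5 puts the eligibility judgement before consent: "Subjects will be screened and interviewed using the inclusion/exclusion criteria and if eligible, be asked" about taking part. Section 6.4 ticks electronic record screening as a recruitment method.

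On the order of steps, Section 8.2 (Instrument Administration) says "Informed consent, randomization and data abstraction/collection will be obtained by the investigators", and Section 8.2 (Randomization) says "Following enrollment, the subject will be assigned in sequential order". The table in Section 8.3 lists consent, then randomization, then the row that begins "Prior to drug administration (zero".

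The Randomization paragraph says that subjects are blinded and is silent on investigators. Under Instrument Administration, investigators also take the bedside pain scores.

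The analysis in Section 8.2 (Statistical Methods) is: "Differences between pain scores at time zero (before drug administration) and at time 30 minutes will be compared" between the two arms. No section requires a time-zero score above 5, a re-check before randomization or dosing, or a rule for a subject who no longer qualifies. No analysis set is defined.

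**The concern.** The score that admits a patient and the score that starts the primary outcome are separate measurements, and the plan does not connect them. Two consequences need to be kept apart.

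The first is room for change. A patient who screens at 7 and stands at 3 at time zero can fall by at most 3 points. Such patients compress the change in both arms. The primary hypothesis in Section 3.0 is that the arms do not differ, so lost sensitivity makes the data look more like the expected answer.

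The second is the integrity of the baseline. If time zero is scored after assignment by someone who may know the arm, the score is not a pre-randomization baseline, and it enters the analysed difference directly.

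**Working it through.** **Order of steps.** The stated total in Section 8.3 reproduces: 30 + 5 + 6 × 10 = 95 minutes. Consent and randomization, listed ahead of time zero, account for 30 + 5 = 35 minutes of activity. Instrument Administration gives the same order in prose (consent, randomization, data collection). Neither passage puts a re-check between them.

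**Share at or below 5 at time zero.** The documents give no data on how pain moves between screening and time zero, so everything here is assumed. For screening score S, mean fall m and SD s of the change, P(time zero ≤ 5) = Φ((5.5 − (S − m))/s). With s = 1.5:

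| S | m = 0 | m = 1.3 |
|---|---|---|
| 6 | 37% | 70% |
| 7 | 16% | 45% |
| 8 | 5% | 21% |
| 9 | 1% | 7% |

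The answer depends heavily on where screening scores lie. With assumed weights of 0.15, 0.20, 0.30, 0.15 and 0.20 on scores 6 to 10, a simulation gave:

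| Mean fall | SD 1 | SD 1.5 | SD 2 |
|---|---|---|---|
| 0 | 6% | 10% | 15% |
| 1 | 19% | 22% | 26% |
| 2 | 38% | 40% | 41% |

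A hand check of the last cell: 0.15 × 0.773 + 0.20 × 0.599 + 0.30 × 0.401 + 0.15 × 0.227 + 0.20 × 0.106 = 0.41. Out of 40 subjects, the range is about 2 to 16 (simulated means 2.5 to 16.4).

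**Cost in sensitivity.** The plan has no power figure to reproduce; the Group Size paragraph sets N = 40 by one year's availability. As an illustration, take 20 per arm, two-sided alpha 0.05, a true difference of 1.3 (the plan's threshold) and an assumed SD of the change. Let a share f contribute no between-arm difference, so the effect is 1.3 × (1 − f) and power ≈ Φ(1.3(1 − f)/(SD × √(2/20)) − 1.96). For SD 2 and f = 0 this is Φ(1.3/0.632 − 1.96) = 54%.

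| f | SD 2 | SD 2.5 | SD 3 | N inflation 1/(1 − f)² |
|---|---|---|---|---|
| 0 | 54% | 38% | 28% | 1.00 |
| 10% | 46% | 32% | 23% | 1.23 |
| 20% | 38% | 26% | 19% | 1.56 |
| 30% | 30% | 21% | 16% | 2.04 |

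For a given f this overstates the loss, because a patient at 5 can still fall by 5 points.

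**Baseline after assignment.** The analysed quantity is NRS at time zero minus NRS at 30 minutes. If knowledge of the arm shifts the recorded time-zero mean by d points in one arm only, the between-arm difference in change shifts by the same d. Randomization does not remove this, because the shift arises after assignment. The documents give no basis for a value of d.

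**The case against.** Several stronger readings are tempting, and the documents do not support them.

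- A reader might infer that patients no longer in qualifying pain are in fact randomized, dosed and analysed. The plan only fails to prevent it. Needing IV medication reads as a current need, the investigators are toxicologists at the bedside who could re-check, and with no analysis set defined, inclusion in the analysis is an inference.
- A reader might take "There will be no restrictions on additional pain medications given" in the Lay Summary to mean that patients will be treated during consent. That sentence follows the description of the study dose and concerns treatment afterwards. The weaker support is that Section 8.2 records earlier analgesia while Section 6.2 lists no washout or recent-analgesic exclusion.
- A reader might take 35 minutes as a minimum interval. Section 8.3 estimates burden for the ethics board; it is not a timed schedule. No section expressly orders the time-zero score against assignment, though the order named in Instrument Administration matches the table.
- A reader might say that a patient at NRS 1 cannot show a 1.3-point difference. In Statistical Methods, 1.3 is a difference between groups, which no single patient can show.
- The percentages are largest at screening scores of 6 and 7, the two lowest eligible. Section 1.0 describes this pain as classically severe, so higher scores are plausible.

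It can also be said that an undated entry score does not bias a randomized comparison, that the study is a feasibility pilot, and that Section 3.0 names the 30-minute score itself as the primary endpoint, in which time zero plays no part.

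The first two of these stand as limits on the entry gap. The third does not dispose of the baseline issue, because the only analysis described uses the difference from time zero.

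**Conclusion.** The point holds in a limited form. Criterion 3 is not tied to time zero, consent and randomization are named before that score, and no re-check is stated. Patients at 5 or below can therefore be randomized and dosed. By itself this costs sensitivity and does not bias the comparison. Its size cannot be fixed from the documents: 6% to 41% of subjects under assumed screening scores, mean falls of 0 to 2 points and SDs of 1 to 2.

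The stronger reason to act is the baseline. Investigators randomize and score, and only subjects are stated to be blinded, so the time-zero score can be influenced by knowledge of the arm, and any such influence passes one for one into the analysed change. The plan does not say that investigators know the arm; it does not say that they do not. The remedy costs almost nothing, so the change should be made.

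**What to change.** Take the time-zero NRS, with RASS, SERSDA and vital signs, after consent and before the assignment is revealed. State in Section 6.2 that this score establishes the existing NRS >5 criterion. Reorder Instrument Administration and the Section 8.3 table to match: consent, time-zero assessments, confirmation of eligibility, randomization, dosing. How a consented patient at 5 or below is then handled is for the investigators to settle and write down.

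No assessment is added. The cost is that some consented patients would not be randomized. That could be more than a few if screening scores cluster at 6 to 7 (16% to 37% with no mean fall and SD 1.5, in the first table above), and N already rests on one year's availability. Selecting on the baseline score also adds regression to the mean. It does so equally in both arms, so it enlarges the change within each arm but not the difference between them.

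The change protects the time-zero score only. The later scores are taken by the same investigators and are not covered by it.
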